9 KEY STATISTICAL CONSIDERATIONS

This section details the principal statistical analysis strategy and procedures for the study. If, after the study has begun, changes are made to the statistical analysis plan stated below, then these deviations to the plan will be listed, along with an explanation as to why they occurred, in the Clinical Study Report.

9.1 Responsibility for Analyses

The statistical analysis of the data obtained from this study will be conducted by, or under the direct auspices of, the Early Clinical Development Statistics Department in collaboration with the Quantitative Pharmacology and Pharmacometrics Department and Translational Medicine Department of the Sponsor.

9.2 Hypotheses/Estimation

Objectives and hypotheses of the study are stated in Section 3 of the protocol.

9.3 Analysis Endpoints

9.3.1 Primary Endpoints

Safety: Primary safety endpoints will include all types of adverse events and discontinuation of study intervention due to adverse event(s), in addition to laboratory safety tests, ECGs, C-SSRS and vital signs. Baseline is defined as measurements obtained pre-dose Day 1.

9.3.2 Secondary Endpoints

Pharmacokinetics: The pharmacokinetic variable(s) of plasma MK-1167 [AUC0-24, Cmax, C24, Tmax, CL/F, Vz/F, t1/2] are of secondary interest.

9.3.3 Exploratory Endpoints

MMSE-2, DSST.

9.4 Analysis Populations

The following populations are defined for the analysis and reporting of data. All participants will be reported, and their data analyzed, according to the treatment(s) they actually received.

9.4.1 All Participants As Treated Population

The All Participants as Treated Population consists of all participants who received at least one dose of treatment. This population will be used for assessments of safety and tolerability.

9.4.2 Per-Protocol (PP) Population

The Per-Protocol Population consists of the set of data generated by the subset of participants who comply with the protocol sufficiently to ensure that these data will be likely to exhibit

the effects of treatment, according to the underlying scientific model. Compliance covers such considerations as exposure to treatment, availability of measurements and absence of important protocol deviations. Important protocol deviations will be identified to the extent possible prior to unblinding by individuals responsible for data collection/compliance, and its analysis and interpretation. Any participants or data values excluded from analysis will be identified, along with their reason for exclusion, in the CSR. At the end of the study, all participants who are compliant with the study procedure as aforementioned and have available data from at least one treatment will be included in the Per-Protocol dataset. This population will be used for the pharmacokinetics and pharmacodynamic analyses.

9.5 Statistical Methods

9.5.1 Statistical Methods for Pharmacokinetic Analyses

Model-based PK summary

CCI

08X3SB

Kenward and Roger's adjustment to the degrees of freedom will be employed. Ninety-five percent confidence intervals for the least squares means by day will be constructed on the natural log scale and will reference a t-distribution. Exponentiating the least-squares means and lower and upper limits of these confidence intervals will yield estimates for the population geometric means and confidence intervals about the geometric means on the original scale. A sample code is as follows:

proc mixed data=adpp; class day usubjid; model lnpk=day /ddfm=kr; random usubjid; lsmeans day /alpha=0.05 cl; run;

To assess the accumulation of MK-1167 relative to the loading dose, the least squares mean differences and 90% confidence intervals from this model will be back transformed to obtain the geometric mean accumulation ratios (Day 8/Day 1 and Day 21/Day 1) and 90% confidence intervals for

Kenward and Roger's adjustment to the degrees of freedom will be employed.

Ninety-five percent confidence intervals for the least squares means by day will be constructed on the natural log scale and will reference a t-distribution. Exponentiating the least-squares means and lower and upper limits of these confidence intervals will yield

estimates for the population geometric means and confidence intervals about the geometric means on the original scale. A sample code is as follows:

proc mixed data=adpp; class day usubjid; model lnpk=day /ddfm=kr; random usubjid; lsmeans day /alpha=0.05 cl; run;

Descriptive Statistics

Individual values will be listed for each PK parameter by treatment, and the following (non-model-based) descriptive statistics will be provided: N (number of participants with non-missing data), arithmetic mean, standard deviation, arithmetic percent coefficient of variation (CV, calculated as $100 \times \text{standard deviation/arithmetic mean}$), median, minimum, maximum, geometric mean, and geometric percent CV (calculated as $100 \times \text{sqrt(exp(s}^2) - 1)$), where s^2 is the observed variance on the natural log-scale).

9.5.2 Statistical Methods for Pharmacodynamic Analyses

MMSE-2 scores

In order to evaluate the change in cognitive function of AD patients, descriptive summary statistics of the values and the change from baseline values will be provided for the MMSE-2 scores obtained at baseline (screening) and from the last day of dosing.

WAIS-IV DSST scores

In order to evaluate the change in cognitive function of AD patients, descriptive summary statistics of the values and the change from baseline values will be provided for the DSST scores obtained at baseline (Day -1) and each postdose timepoint by treatment.

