| Urine or Serum Pregnancy Test (POCBP only) | X | X | | | | | | | | | | | | | | Urine test will be collected. Serum test will be collected in the event that urine test is positive or cannot be confirmed. Section 5.1, Appendix 2 |
| HIV, Hepatitis B and C Screen (per site SOP) | X | | | | | | | | | | | | | | | Section 5.2, Appendices 2, 8 |
| UDS/BDS (per site SOP) | X | Xf | | | | | | | | | | | | | | Drug screen is mandatory at Screening; any additional drug screen(s) is/are conducted per site SOP. Section 8.3.4, Appendix 2 |
| Alcohol Screen | X | X | | | | | | | | | | | | | | Breathing test. Section 5.2, Appendix 2 |
| Clinical Safety Assessment (Hematology, Urinalysis, and Chemistry) | X | X | | X | | Х | | X | | | X | | | | X | Screening, Day -3, and Poststudy visits: anytime. CCI Section 8.3.4, Appendices 2 and 8 |
| AE/SAE Review | 2 | X | | | | | | | | | | | | X | | Section 8.4, Appendix 3 |
| MMSE-2 | X | | | | | | | X^{l} | | | | | | | | Sections 5.1, 5.2, 8.3.6 |
| DSST ^m | X | | X | | X^{i} | X | | X | | Xn | X | | | | X | Sections 4.2.1.3, 8.3.7, 8.7 |
| C-SSRS Baseline ^o | X | | | | | | | | | | | | | | | Sections 4.2.3, 5.2, 8.3.8 |
| C-SSRS Since Last Assessment ^o | | | | X | | X | Xe | X | X | | X | | | | X | Sections 4.2.3, 8.3.8 |

| | | | | | | | | | | | | Pane | l B | | | | | | | | |
|--|------------------------|-----|---|---|---|---|---|---|---|---|---|------|-----|---------------------------|----------------|----------------|---------------------------|----------------|-----------|------------------------|---|
| Study Period | ning ^a | CCI | | | | | | | | | | | | | | | | | | udy ^b | Notes |
| Study Day | Screening ^a | | | | | | | | | | | | | | | | | | | Poststudy ^b | |
| Pharmacokinetics | - | | | | | | | | | | | | | | | | | | | | |
| Blood for Plasma MK-1167 and Metabolites Assaying | | | | | X | X | X | X | X | X | X | X | X | \mathbf{X}^{j} | X ^j | X ^j | \mathbf{X}^{j} | X ^j | $X^{j,k}$ | | Sections 8.6.1, 8.10.5, Appendix 8 |
| Blood for Plasma Donepezil Assaying ^p | | X | X | X | | | | | | | | | X | | | | | | | | Day 2: 24 hours postdose ^g . Day 2: 0.5, 1, 2, 3, 4, 6, 8, 12, and 24 hours postdose ^g . Day 3: predose and 0.5, 1, 2, 3, 4, 6, 8, 12, 24 hours postdose. Section 8.10.5, Appendix 8 |

| | | | | | | | | Pane | el B | | | | | |
|----------------------------|--------|-----|--|---|--|---|--|------|------|--|--|--|------------------------|--|
| Study Period | inga | CCI | | | | | | | | | | | udy ^b | Notes |

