| Study Day | Screen | | | | | | | | | | | | Poststudy ^b | |
| Biomarkers | | | | | | | | | | | | | | |
| Blood for Genetic Analysis | | | | X | | | | | | | | | | Predose from enrolled participants only. Section 8.8, Appendix 8. |
| CCI | X | | | | | - | | | | | | | | Sections 8.8, 8.10.1, and Appendix 8 |

AE=adverse event; BDS=blood drug screen; BMI=body mass index; CRU=Clinical Research Unit; C-SSRS=Columbia-Suicide Severity Rating Scale; CYP=cytochrome P450; DSST=Digit Symbol Substitution Test; ECG=electrocardiogram; FBR=future biomedical research; FSH=follicle-stimulating hormone; HIV=human immunodeficiency virus; ID=identification; MMSE-2=Mini-Mental State Examination Edition 2; PK=pharmacokinetic(s); POCBP=participant of childbearing potential; PONCBP=participant of nonchildbearing potential; SAE=serious adverse event; SOP=standard operating procedure; UDS=urine drug screen; VS=vital signs.

[figure not shown]
- ^a Screening should occur within 4 weeks prior to Day 1.
- The Poststudy Visit will occur at approximately days after last dose.
- Donepezil will be administered in the mornings at approximately the same time as MK-1167/placebo. If participants do not usually take their donepezil in the mornings, they should be instructed to start taking it in the morning starting on Day -7 until Day -4. On Days donepezil will be dispensed and administered by site staff.
- d Standardized meals/snacks will be provided on all days during domiciling at ~ 2 (breakfast), ~ 4 (lunch), ~ 7 (snack), ~ 10 (dinner), and ~ 13 (snack) hours postdose or equivalent (Section 5.3.1).
- e Day 16 only.
- f Can be conducted within 24 hours prior to first dose.
- g 24-hour timepoint will be collected at predose when dosing occurs on the day of collection.
- ECG measurements to be obtained in triplicate and performed before any blood sample for each timepoint.
- i Day 2 only.
- Participants will return to the clinic for collection of MK-1167 plasma samples and ECG recordings at the hours/days specified in the Schedule of Activities.
- b Day scheduled study procedures collected before any Poststudy Visit procedures.
- Within 12 hours of morning dose.
- M A practice assessment will be administered at Screening. The assessment given on Day -1 will provide the baseline value. On Days should be given within 4 hours after the morning dose. See Study Operation's Manual for specific instructions on test administration.
- n CCI

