3 HYPOTHESES, OBJECTIVES, AND ENDPOINTS

Hypotheses are aligned with objectives in the Objectives and Endpoints table.

The study population consists of patients with mild to moderate AD, 50 to 90 years of age.

| Primary Objective | Primary Endpoint |
|---|--|
| Evaluate the safety and tolerability of MK-1167 when administered to patients with mild to moderate Alzheimer's Disease on stable doses of oral donepezil 10 mg daily | Adverse events, discontinuation due to Adverse events |
| Secondary Objectives | Secondary Endpoints |
| Evaluate the pharmacokinetic profile of MK-1167 when administered to patients with mild to moderate Alzheimer's Disease on stable doses of oral donepezil 10 mg daily Estimation: | AUC0-24, Cmax, C24, Tmax, CL/F, Vz/F, t1/2 |
| Tertiary/Exploratory Objectives | Tertiary/Exploratory Endpoints |
| Evaluate the changes in cognitive function of Alzheimer's Disease patients by comparing the Mini Mental State Examination and Digit Symbol Substitution Test scores obtained at baseline with those from the last day of dosing. | Mini Mental State Examination scores Digit Symbol Substitution Test scores |
| CCI | Germline genetic variation |
| Explore the relationships between genetic variation, response to the treatment(s) administered, and mechanisms of disease. Variation across the human genome may be analyzed for association with clinical data collected in the study. | Germline genetic variation |

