4 STUDY DESIGN

4.1 Overall Design

This is a randomized, double-blind, placebo-controlled, multisite study to evaluate the safety, tolerability, and PK of multiple doses of MK-1167 in participants with Alzheimer's disease maintained on baseline AChEI treatment with donepezil 10 mg PO daily.

Specific procedures to be performed during the study, including prescribed times and associated visit windows, are outlined in Section 1.3 of the SoA. Details of each procedure are provided in Section 8.

In Panel A, participants will receive a loading dose of MK-1167 6 mg or matching PBO on Days 1 to 7 followed by QD dosing of MK-1167 3 mg or matching PBO for 14 consecutive days (Days 8 to 21). In Panel B, participants will receive QD dosing of MK-1167 6 mg or matching PBO for Days 1 to 31

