10.8 Appendix 8: Blood Volume Tables

Panel A

| | Pre- Study ^a | Treatment Periods | Post- Study | Total Collections | mL Per Collection | Total mL/Test |
|--|----------------------------|----------------------|----------------|----------------------|----------------------|------------------|
| Laboratory Safety Tests | 1 | 4 | 1 | 6 | 12.5 | 75 |
| HIV/Hepatitis Screen (at the discretion of the investigator) | 1 | 0 | 0 | 1 | 5 | 5 |
| Blood for Planned Genetic Analysis | 0 | 1 | 0 | 1 | 8.5 | 8.5 |
| CCI | 1 | 0 | 0 | 0 | 5 | 5 |
| Blood for donepezil PK | 11 | 10 | 0 | 21 | 3 | 63 |
| Blood for MK-1167 PK | 0 | 51 | 0 | 51 | 4 | 204 |
| Total Blood Volume per Participant ^b | | | 360.5 | | | |

^a Pre-Study includes screening and Days -3, -2, and -1.

Panel B

| | Pre- Study ^a | Treatment Periods | Post- Study | Total Collections | mL Per Collection | Total mL/Test |
|--|----------------------------|----------------------|----------------|----------------------|----------------------|------------------|
| Laboratory Safety Tests including serum hCG (POCBP) or serum FSH (PONCBP) and BDS | 1 | 5 | 1 | 7 | 12.5 | 87.5 |
| HIV/Hepatitis Screen (at the discretion of the investigator) | 1 | 0 | 0 | 1 | 5 | 5 |
| Blood for Planned Genetic Analysis | 0 | 1 | 0 | 1 | 8.5 | 8.5 |
| CCI | 1 | 0 | 0 | 0 | 5 | 5 |
| Blood for donepezil PK | 11 | 10 | 0 | 21 | 3 | 63 |
| Blood for MK-1167 PK | 0 | 61 | 0 | 61 | 4 | 244 |
| Total Blood Volume per Participant ^b | | | 413 | | | |

^a Pre-Study includes screening and Days -3, -2, and -1.

b If additional pharmacokinetic and/or safety analysis is necessary, additional blood (no more than 50 mL in total) may be obtained.

b If additional pharmacokinetic and/or safety analysis is necessary, additional blood (no more than 50 mL in total) may be obtained.

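### The Panel B schedule, as published, appears to place the only post-screening MMSE-2 before the last dosing day, which Sections 3 and 9.5.2 require

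*Combined protocol and SAP*

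**What the plan says.** The exploratory objective in Section 3 compares MMSE and DSST "scores obtained at baseline with those from the last day of dosing". Section 9.5.2 carries this into the analysis as descriptive summaries of values and change for "MMSE-2 scores obtained at baseline (screening) and from the last day of dosing". Neither section excepts a panel.

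Section 4.1 gives Panel B "QD dosing of MK-1167 6 mg or matching PBO for Days 1 to 31", so its last dosing day is Day 31. Panel A ends on Day 21.

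In the Section 1.3 table for Panel B, the MMSE-2 row has a mark at Screening and one later mark with a footnote. From that later mark to the end, the row reads "X^{l} | | | | | | | | Sections 5.1, 5.2, 8.3.6". By its place in the footnote list, the footnote reads "Within 12 hours of morning dose". The DSST row of the same table ends "X^{i} | X | | X | | Xn | X | | | | X | Sections", so it has marks well beyond the MMSE-2 one.

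**The concern.** The analysis needs an MMSE-2 on the last dosing day in each panel. The Panel B schedule seems to collect its one on-treatment MMSE-2 at an earlier visit. A site following the table would then produce no value for the defined endpoint in the panel with the longer treatment and the higher continuing dose. Section 9.5.2 does not say whether the panels are summarised together. If they were, an end-of-treatment change in Panel A and a mid-treatment change in Panel B would carry the same label. A last-day score that was not taken cannot be recovered later.

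**Working it through.** No sample-size or power figure is involved. The check is a reading of the schedule grid. Cells are counted between the row label and the Notes cell, with Screening as column 1.

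**Panel B marks.** The segment holding MMSE-2 has 15 columns, and column 15 is Poststudy.
- MMSE-2: 1, 8
- Laboratory tests: 1, 2, 4, 6, 8, 11, 15
- ECG: 1, 4, 5, 6, 8, 11, 13, 14
- DSST: 1, 3, 5, 6, 8, 10, 11, 15
- C-SSRS (since last assessment): 4, 6, 7, 8, 9, 11, 15

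**Is the grid read correctly?** Appendix 8 gives an independent count for one row: "Laboratory Safety Tests including serum hCG (POCBP) or serum FSH (PONCBP) and BDS | 1 | 5 | 1 | 7".
- Panel B: the schedule shows 7 laboratory marks, and 1 + 5 + 1 = 7. At 12.5 mL each, 7 × 12.5 = 87.5 mL, as stated.
- Panel A: the marks are in columns 1, 2, 4, 6, 8 and 12 of 12, which is 6 = 1 + 4 + 1, and 6 × 12.5 = 75 mL, as stated.
- In both panels the split between pre-study and treatment works only if the column 2 (Day -3) draw is counted under treatment. The totals do not depend on that.

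The column 11 laboratory mark is needed to reach 7.

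**Where column 8 falls.** The C-SSRS mark in column 7 is footnoted as Day 16 only. Column 8 comes next, and its MMSE-2 footnote makes it a dosing day. It therefore lies after Day 16 and no later than Day 31. Later columns still carry assessments: C-SSRS in 9, DSST in 10, and all four comparison rows in 11.

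**Whether column 11 is on treatment.** Four observations point that way:
1. The footnote "Participants will return to the clinic for collection of MK-1167 plasma samples and ECG recordings" (letter j by order in the list) is attached to the ECG marks in columns 13 and 14, but not to column 11.
2. The physical and targeted neurological examination rows sit in an adjoining segment of 16 columns. Their Day-16-only mark is in column 8, followed by marks in 9 and 12. Those steps (+1, +3) match 7 to 8 to 11 here.
3. Counting back from Poststudy, Panel A's last on-treatment assessment column is 12 − 8 = 4 columns earlier. In Panel B, 15 − 11 = 4.
4. Section 8.1.11 names Days 23 and 31 as days on which Panel B participants may stay overnight. Two late assessment days fit columns 8 and 11, although the document does not make that link.

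**Panel A for comparison.** MMSE-2 is in columns 1, 8 and 12. Column 8 directly follows a DSST mark footnoted as Days 17 to 20, and its own MMSE-2 footnote makes it a dosing day. That fits Day 21, the last dosing day, so Panel A meets Sections 3 and 9.5.2.

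**Size, if column 11 is Day 31.** Tables 4 and 5 allocate 12 + 4 = 16 participants to Panel A and 9 + 3 = 12 to Panel B.
- All participants without a last-day MMSE-2: 12 / (16 + 12) = 12/28 = 43%.
- On MK-1167: 9 / (12 + 9) = 9/21 = 43%.

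**The case against.** The strongest objection is that the deciding fact is redacted. No Panel B day heading is visible, the footnote on the column 10 DSST mark is blacked out, and the MMSE-2 footnote shows only that column 8 is a dosing day. That stands: the calendar dates of columns 8 and 11 are inferred.

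The MK-1167/placebo administration row is a second difficulty. It ends in column 9 of a segment with 14 columns. Aligned on Day 1 (column 4 in both segments), that end falls at column 9. Aligned on Poststudy, it falls at 15 − (14 − 9) = column 10. Neither is column 11, so the row does not confirm that column 11 is Day 31. But both are later than column 8, so the row does not support column 8 as the last dosing day either. With differing column counts it is weak evidence in any direction.

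Third, marks are lost elsewhere in the extracted tables. For example, the Panel A orthostatic vital-sign row has a note about the Poststudy visit but no mark there. The Appendix 8 check validates the laboratory row, and no comparable count exists for MMSE-2. A dropped mark is therefore possible, though the rows in this segment all have the same 15 columns.

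A reader might also infer that the row was copied from Panel A without adjustment. The documents do not show this: a copied row would have kept Panel A's Poststudy mark, which Panel B lacks. Nor is the missing Poststudy MMSE-2 a defect in itself, because the planned MMSE-2 analysis uses only screening and the last dosing day.

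**Conclusion.** The point holds as an apparent mismatch between the Panel B schedule and the endpoint definition in Sections 3 and 9.5.2, to be confirmed against the unredacted table. It rests on two assumptions: that the published MMSE-2 row has lost no mark, and that column 8 is earlier than Day 31. The second is well supported by the later assessment columns. That column 11 is itself Day 31 is likely but not shown.

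A reader might take it as established that 12 of 28 participants will have no last-day MMSE-2. The documents do not support that flat statement, because the figure is conditional on the column reading. The consequence is also bounded: MMSE-2 change is exploratory and summarised descriptively with no hypothesis, and DSST, the other cognitive measure, is marked in column 11. The primary safety and secondary pharmacokinetic analyses are not affected.

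**What to change.** Check the Panel B MMSE-2 row against the unredacted schedule. If the last dosing day carries no mark, do one of two things:
- Move the existing mark to the last dosing day, or add one there.
- State in Sections 3 and 9.5.2 that the Panel B MMSE-2 change is from screening to the day it is actually collected, naming that day. Report it separately from Panel A rather than pooling both as a last-dosing-day change.

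The first is one edit to the table. Moving the mark adds no assessment, and adding one costs a single short paper test per participant. The second is a text edit, and is the only option for participants who have already completed dosing. No Poststudy MMSE-2 needs to be added.

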9.5.3 Statistical Methods for Safety Analyses

Safety will be evaluated by clinical assessment of AEs, 12-lead ECGs, vital signs, laboratory safety tests, physical/neurological examinations and C-SSRS. Summary statistics and plots will be generated for raw laboratory safety tests, ECGs, and/or VS as well as for change from

baseline, as deemed clinically appropriate. Depending on the safety parameter, the difference from baseline will either be computed on the original scale (raw change from baseline) or on the log scale and back-transformed for reporting (percent change from baseline). Responses to the C-SSRS will be tabulated and the individual score will be listed.

9.6 Interim Analyses

No interim analysis is planned.

9.7 Multiplicity

08X3SB

Since there is no hypothesis, no adjustments for multiplicity are needed.

9.8 Sample Size and Power Calculations

10 SUPPORTING DOCUMENTATION AND OPERATIONAL CONSIDERATIONS

10.1 Appendix 1: Regulatory, Ethical, and Study Oversight Considerations

10.1.1 Code of Conduct for Interventional Clinical Trials

Merck Sharp & Dohme LLC, Rahway, NJ, USA (MSD)

I. Introduction

A. Purpose

Merck Sharp & Dohme LLC, Rahway, NJ, USA (MSD), through its subsidiaries, conducts clinical trials worldwide to evaluate the safety and effectiveness of our products. As such, we are committed to designing, planning, conducting, analyzing, and reporting these trials in compliance with the highest ethical and scientific standards. Protection of participants in clinical trials is the overriding concern in the design and conduct of clinical trials. In all cases, MSD clinical trials will be conducted in compliance with MSD's global standards, local and/or national regulations (including all applicable data protection laws and regulations), and International Council for Harmonisation Good Clinical Practice (ICH GCP) E6 and ICH General Considerations for Clinical Studies E8, and in accordance with the ethical principles that have their origin in the Declaration of Helsinki.

B. Scope

Highest ethical and scientific standards shall be endorsed for all clinical interventional investigations sponsored by MSD irrespective of the party (parties) employed for their execution (e.g., contract research organizations, collaborative research efforts). This Code is not intended to apply to trials that are observational in nature, or which are retrospective. Further, this Code does not apply to investigator-initiated trials, which are not under the full control of MSD.

II. Scientific Issues

A. Trial Conduct

1. Trial Design

Except for pilot or estimation trials, clinical trial protocols will be hypothesisdriven to assess safety, efficacy, and/or pharmacokinetic or pharmacodynamic indices of MSD or comparator products. Alternatively, MSD may conduct outcomes research trials, trials to assess or validate various endpoint measures, or trials to determine patient preferences, etc.

The design (i.e., participant population, duration, statistical power) must be adequate to address the specific purpose of the trial and shall respect the data protection rights of all participants, trial site staff and, where applicable, third parties. Input may be considered from a broad range of stakeholders, including patient advocacy groups/patients representing the trial population, caregivers, and healthcare providers to ensure operational feasibility. Trial design also includes

proactive identification of critical to quality factors utilizing a risk-based approach. Plans are then developed to assess and mitigate risks to those factors as appropriate during the trial. All trial protocols are and will be assessed for the need and capability to enroll underrepresented groups. Participants must meet protocol entry criteria to be enrolled in the trial.

2. Site Selection

MSD's clinical trials are conducted globally in many different countries and in diverse populations, including people of varying age, race, ethnicity, gender, and accounting for other potential disease related factors. MSD selects investigative sites based on medical expertise, access to appropriate participants, adequacy of facilities and staff, previous performance in clinical trials, as well as budgetary considerations. Prior to trial initiation, sites are evaluated by MSD personnel (or individuals acting on behalf of MSD) to assess the ability to successfully conduct the trial. Individuals involved in trial conduct receive training commensurate with their role prior to their becoming involved in the trial.

Where appropriate, and in accordance with regulatory authority guidance, MSD will make concerted efforts to raise awareness of clinical trial opportunities in various communities. MSD will seek to engage underrepresented groups and those disproportionately impacted by the disease under study. MSD will support clinical trial investigators to enroll underrepresented groups and expand access to those who will ultimately use the products under investigation.

3. Site Monitoring/Scientific Integrity

Investigative trial sites are monitored to assess compliance with the trial protocol and Good Clinical Practice (GCP). MSD reviews clinical data for accuracy, completeness, and consistency. Data are verified versus source documentation according to standard operating procedures. Per MSD policies and procedures, if potential fraud, scientific/research misconduct, privacy incidents/breaches or Clinical Trial-related Significant Quality Issues are reported, such matters are investigated. When necessary, appropriate corrective and/or preventative actions are defined and regulatory authorities and/or ethics review committees are notified.

B. Publication and Authorship

Regardless of trial outcome, MSD commits to publish the primary and secondary results of its registered trials of marketed products in which treatment is assigned, according to the pre-specified plans for data analysis. To the extent scientifically appropriate, MSD seeks to publish the results of other analyses it conducts that are important to patients, physicians, and payers. Some early phase or pilot trials are intended to be hypothesis generating rather than hypothesis testing; in such cases, publication of results may not be appropriate since the trial may be underpowered and the analyses complicated by statistical issues such as multiplicity.

MSD's policy on authorship is consistent with the recommendations published by the International Committee of Medical Journal Editors (ICMJE). In summary, authorship should reflect significant contribution to the design and conduct of the trial, performance or interpretation of the analysis, and/or writing of the manuscript. All named authors must be able to defend the trial results and conclusions. MSD funding of a trial will be acknowledged in publications.

III. Participant Protection

A. Regulatory Authority and Ethics Committee Review (Institutional Review Board [IRB]/Independent Ethics Committee [IEC])

All protocols and protocol amendments will be submitted by MSD for regulatory authority acceptance/authorization prior to implementation of the trial or amendment, in compliance with local and/or national regulations.

The protocol, protocol amendment(s), informed consent form, investigator's brochure, and other relevant trial documents must be reviewed and approved by an IRB/IEC before being implemented at each site, in compliance with local and/or national regulations and ICH Guidelines. Changes to the protocol that are required urgently to eliminate an immediate hazard and to protect participant safety may be enacted in anticipation of ethics committee approval. MSD will inform regulatory authorities of such new measures to protect participant safety, in compliance with local and/or national regulations.

B. Safety

The guiding principle in decision-making in clinical trials is that participant welfare is of primary importance. Potential participants will be informed of the risks and benefits of, as well as alternatives to, trial participation. At a minimum, trial designs will take into account the local standard of care.

All participation in MSD clinical trials is voluntary. Participants enter the trial only after informed consent is obtained. Trial designs include procedures and systems for the identification, monitoring, and reporting of safety concerns. Participants may withdraw from an MSD trial at any time, without any influence on their access to, or receipt of, medical care that may otherwise be available to them.

During trial planning, the need for an independent Data Monitoring Committee (DMC) is assessed. DMC review of data accumulated during the conduct of the trial is integral to the well-being of trial participants.

C. Confidentiality

MSD is committed to safeguarding participant confidentiality, to the greatest extent possible, as well as all applicable data protection rights. Unless required by law, only the investigator, Sponsor (or individuals acting on behalf of MSD), ethics committee, and/or regulatory authorities will have access to confidential medical records that might identify the participant by name.

D. Genomic Research

Genomic research will only be conducted in accordance with a protocol and informed consent authorized by an ethics committee.

E. Trial Results

At the time of providing informed consent and in accordance with local laws and regulations, participants should be informed about the plans for availability of trial results.

IV. Financial Considerations

A. Payments to Investigators

Clinical trials are time- and labor-intensive. It is MSD's policy to compensate investigators (or the sponsoring institution) in a fair manner for the work performed in support of MSD trials. MSD does not pay incentives to enroll participants in its trials. However, when enrollment is particularly challenging, additional payments may be made to compensate for the time spent in extra recruiting efforts.

MSD does not pay for participant referrals. However, MSD may compensate referring physicians for time spent on medical record review and medical evaluation to identify potentially eligible participants.

B. Clinical Research Funding

Informed consent forms will disclose that the trial is sponsored by MSD, and that the investigator or sponsoring institution is being paid or provided a grant for performing the trial. However, the local ethics committee may wish to alter the wording of the disclosure statement to be consistent with financial practices at that institution. As noted above, all publications resulting from MSD trials will indicate MSD as a source of funding.

C. Funding for Travel and Other Requests

Funding of travel by investigators and support staff (e.g., to scientific meetings, investigator meetings, etc) will be consistent with local guidelines and practices.

V. Investigator Commitment

Investigators will be expected to review MSD's Code of Conduct as an appendix to the trial protocol, and in signing the protocol, agree to support these ethical and scientific standards.

